#### 1.0 BACKGROUND AND RATIONALE:

Each year in the U.S., an estimated 2 million women (~6,000 women each day) reach the critical stage of female reproductive aging known as menopause [1]. Menopause is characterized by the permanent cessation of menses and the loss of ovarian follicular activity brought about by the decline in 17 $\beta$ -estradiol (i.e., estrogen deficiency). Among American women, the median age of menopause is 51 y [1]. Based on a current life expectancy of 80.5 yrs [2], women in this country can expect to spend up to one-third of their lifetime in this postmenopausal stage.

The impact of decreasing 17 $\beta$ -estradiol on immune cell function, especially some T cell populations, has become the focus of much women's health research. It is widely accepted that after menopause women exhibit a significant increase in their risk for chronic diseases, including gynecologic and breast cancers, autoimmune diseases, cardiovascular disease, and osteoporosis [3, 4]. In terms of bone health, which is the focus of our laboratory's work, postmenopausal women are 4 times more likely to fracture compared to pre-menopausal women (age 20-50 yrs) [5]. Moreover, 1 in 3 women over the age of 50 y will experience an osteoporotic fracture [6]. The decline in 17 $\beta$ -estradiol that occurs with menopause is accompanied by immunological changes in CD4 $^{+}$  effector T cells, most notably an increase in T helper cells expressing the pro-inflammatory cytokine, interleukin (IL)-17 (i.e., Th17 cells) relative to the immunosuppressive, T regulatory (Treg) cells [3, 7, 8]. Th17 cells are highly potent promoters of osteoclastogenesis and accelerate the bone resorption that occurs in estrogen deficiency [9-11]. In contrast, the osteoprotective role of Tregs, which are reported to either decrease or remain unchanged in with menopause, is less clear in humans beyond their anti-inflammatory properties. Consequently, it is the increase in Th17 cells that is the major determinant of the altered Treg/ Th17 ratio that is reported in response to declining estrogen and has a central role in the pathophysiology of postmenopausal osteoporosis [12, 13].

Recent evidence has revealed that the gut microbiota is a critical regulator of this osteoimmunologic (i.e., T cell) response; thus, establishing the gut-bone axis as a viable target to prevent estrogen deficiency-induced bone loss [14-16]. Clinical studies have shown that utilizing probiotics and prebiotics to alter the gut microbiota has beneficial effects on bone and mineral metabolism [17-23]. In animal models of postmenopausal osteoporosis, probiotics and prebiotics increase gut-derived metabolites (e.g., short chain fatty acids [SCFA]), program more tolerogenic or anti-inflammatory immune responses, while preventing bone loss [24-30]. Our laboratory's extensive work on dried plum and its unique ability to not only prevent, but also reverse bone loss in animal models, has revealed that it improves T cell function *ex vivo* and both its polyphenolic and carbohydrate components contribute to its prebiotic activity [31, 32]. These findings combined with strong clinical evidence in support of dried plum's ability to prevent postmenopausal bone loss [33-35] make it an excellent prebiotic candidate to test whether these gut-mediated changes in immune function observed in animal models translate to human subjects.

In addition to age-related changes in estrogen, other factors affecting the T cell biology of postmenopausal women (e.g., vitamin D status) could further compound their osteoporosis risk. Among U.S. women age

51-70 yrs, 28% are vitamin D insufficient and 10% are vitamin D deficient based on the Institute of Medicine guidelines [36]. Although vitamin D is known for its role in skeletal health, evidence of its important extraskeletal functions continues to emerge [37-40]. 1,25-(OH)2D3 simultaneously inhibits the pro-inflammatory Th17 cell and increases the anti-inflammatory Treg cell, number and function [40-44]. Furthermore, vitamin D's influence on immune function has been recently linked, albeit indirectly, to the gut microbiota [45, 46]. Thus, postmenopausal women who have compromised vitamin D status may face even greater risk of T cell-mediated pathologies (e.g., autoimmune diseases & osteoporosis), which further highlights the importance of targeting the gut microbiota.

## 2.0 PROJECT GOALS AND OBJECTIVES:

The goal of this project is to understand how dietary supplementation with dried plums, a food with prebiotic activity, affects T effector cells (i.e., Th17 & Treg) and their function; and to explore whether vitamin D status of the host alters this response. The fundamental questions to be addressed are: 1) whether the findings of pre-clinical studies [26, 28, 47, 48] demonstrating the gut microbiota is a target to counter T cell changes associated with estrogen deficiency translate to postmenopausal women; and 2) whether the vitamin D status of the host influences the response to this prebiotic.

To accomplish this, we will recruit postmenopausal women, age 60-75 years, to participate in a randomized crossover control study with and without dried plum. Eligible volunteers who are willing to consume dried plum per day (5-6 dried plums/d), participate in an ~ 14-wk study, and meet all other inclusion/exclusion criteria, will be consented. We plan to enroll n>=30 women.

The *hypothesis* is that dried plum will have anti-inflammatory effects on the gut-bone axis of postmenopausal women, characterized by a decrease in the abundance of Th17 cells (i.e., increase in Treg/Th17 ratio) and their activation; and this response will be more pronounced in women with higher serum 25(OH) D. To date, there are no reports indicating how dried plum affects the abundance and function of Th17 cells, which accelerate bone resorption by osteoclasts that leads to postmenopausal bone loss and the influence of vitamin D on this response. To test our hypothesis, we will perform a randomized crossover control study designed to:

**Objective 1.** Determine how dried plum supplementation alters circulating T cells (e.g., Th17 & Treg cells), other immune cells that regulate T cell function (e.g., B regulatory cells), and the inflammatory response of postmenopausal women compared to a control period in a crossover design study. *Peripheral blood mononuclear cells (PBMC) will be isolated from whole blood collected pre- and post- treatment of each arm of the study and the change in T cell populations and their function as well as inflammatory mediators in response to dried plum will be assessed.*

**Objective 2.** Assess the changes in the gut microbiota and gut-derived metabolites in response to dried plum compared to the control in stool and serum samples collected pre- and post each treatment arm. *Stool and serum samples will be collected and the change in gut microbiota taxa and fecal and serum metabolites in response to dried plum will be determined.*

**Objective 3.** Determine whether: a) serum vitamin D influences the immune, metabolite and microbiota response to dried plum; and b) the relationship of the immune, metabolite and microbiota outcomes to the bone resorption marker, c-terminal telopeptide 1 (CTX-1) and bone formation markers such as procollagen type 1 N-terminal peptide (PINP). *Serum 25(OH)vitamin*

*D and bone biomarkers (e.g., CTX-1 and PINP) will be assessed and their relationship to outcomes from Objective 1 & 2 will be explored.*

### **3.0 OUTCOME MEASURES AND ENDPOINTS:**

The **primary outcomes** of this study will be change in circulating Th17 cells and their function in *ex vivo* experiments, and inflammatory cytokines (e.g., IL-6 & IL-17).

**Secondary outcomes** will include alterations in circulating Treg cells, their function and Th17/Treg ratio, other immune cells that affect T cells (e.g., B regulatory cells and natural killer cells), serum and fecal metabolites, microbiota taxa, and serum 25(OH)D, cytokines (e.g., TNF- $\alpha$  & IL-10), and the bone resorption and formation markers (e.g., CTX-1 and P1NP).

### **4.0 ELIGIBILITY CRITERIA:**

#### *Inclusion Criteria.*

- women 60-75 years of age at the start of the study;
- 12 or more consecutive months without a menstrual period;
- willing to include dried plums in their daily diet and collect fecal samples at four time points;
- ambulatory without assistance;
- capacity to give informed consent.

#### *Exclusion Criteria.*

- women who have been on medications known to alter bone or calcium metabolism (e.g., oral bisphosphonates, raloxifene, denosumab, intermittent parathyroid hormone, growth hormone) within 12 months of starting the study. Prior use of intravenous bisphosphonates at any time.
- women who have been on hormone replacement therapy, steroids (i.e., glucocorticoids), biologics, or chronic NSAID within 3 months of starting the study.
- women with a previous diagnosis of osteoporosis (i.e., BMD T-score or history of vertebral fracture or fragility fractures of hip, wrist, humerus after the age of 50 yr) or other metabolic bone disease (e.g., osteomalacia or osteogenesis imperfect), renal disease, stroke, heart attack, type 2 diabetes, liver disease or autoimmune diseases (e.g., rheumatoid arthritis, systemic Lupus erythematosus, type 1 diabetes mellitus, IBD) that could affect bone metabolism or T cell biology will be excluded.
- women who have undergone treatment for cancer within 12 months of starting the study
- women who have been taking prebiotic or probiotic supplements or natural products that have estrogen-like effects in the past 3 months
- women who smoke, have a BMI  $>40$  kg/m $^2$  or  $<18.5$  kg/m $^2$ , or consume  $\geq 2$  alcoholic drinks per day
- women who regularly consume dried plums or prune juice ( $>1$  serving weekly).

[figure not shown]

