## 8.0 STUDY PROCEDURES:

**Health and Medical History.** Relevant medical history will be obtained at Visit 1 by the Study Coordinator. The information collected will include a brief medical history, questions related to health behaviors, reproductive history, bone health history (i.e., incidence of previous fractures), prior oral contraceptive and hormone replacement use, as well as the use of other medications and supplements (*See Medical History Form*). The health and medical history will be updated at each subsequent visit to account for any changes occurring over the course of the study. Any concerns raised will be brought to the attention of the CRC staff physician for recommendations.

**FIT Core.** At Visit 1, participants will complete assessments at the FIT Core (IRB study #1707550885). This will include but is not limited to providing additional information related to their medical history, medications, and body composition (height, weight). They will be asked to answer questionnaires regarding their physical function and physical activity and will undergo a DEXA or bone density test. Participants will also be asked to complete a battery of tests related to their physical capacity, including hand grip strength, repeated chair stands, gait speed, timed up-and-go, a six-minute walk test, and a balance assessment.

**Blood Sample Collection.** Participants will provide fasting blood specimens, collected between 7:30-10:00 AM at baseline and final time points in each period (Visit 2-5). Whole blood (~21 mL) will be collected in CPT tubes (BD Biosciences) for FACS analyses and *ex vivo* experiments with PBMCs to characterize Th17 and Treg abundance and function. One additional tube (~5 mL) will be collected and processed for serum, and stored at -80°C for metabolomics, cytokines, 25(OH)D and bone biomarkers.

**Fecal Sample.** Participants will be asked to collect 2 stool samples prior to each visit (Visits 2-5) using a sample collection kit (DNA GeneTek). They will be also asked to rate their stool consistency using the Bristol Stool Scale, as well as ease of passage using a 5-point Likert scale (1 = very easy, 2 = easy, 3 = neither easy nor difficult, 4 = difficult, 5 = very difficult) as we have previously reported [49].

**Anthropometric Measurements.** Height and weight will be assessed at each visit and body mass index (BMI kg/m^2) calculated.

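### Recent systemic antibiotic use is not excluded although prebiotic and probiotic supplements are, which costs precision in the secondary microbiota and metabolite outcomes

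*Protocol*

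**What the plan says.** Protocol Section 4.0 sets the exclusions. Three bullets deal with drugs or supplements that could disturb the outcomes:

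- a 12-month window for "women who have been on medications known to alter bone or calcium metabolism";
- a 3-month window for "women who have been on hormone replacement therapy, steroids (i.e., glucocorticoids), biologics, or chronic NSAID within 3 months of starting the study";
- a 3-month window for "women who have been taking prebiotic or probiotic supplements or natural products that have estrogen-like effects in the past 3 months".

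Antibiotics appear in none of them, nor in any other operative section. The only mention is in the title of a cited reference.

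The microbiota matters to this trial in three places. Section 1.0 states that "the gut microbiota is a critical regulator of this osteoimmunologic (i.e., T cell) response". Objective 2 in Section 2.0 is to "Assess the changes in the gut microbiota and gut-derived metabolites in response to dried plum compared to the control". Section 3.0 lists "serum and fecal metabolites, microbiota taxa, and serum 25(OH)D" among the secondary outcomes. Section 11.0 then uses metabolite and microbiota profiles in an exploratory mediation analysis of the immune response.

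Medication use is recorded. The Visit 1 history in Section 8.0 covers reproductive and bone history "as well as the use of other medications and supplements", and "The health and medical history will be updated at each subsequent visit to account for any changes occurring over the course of the study". No eligibility rule is attached to an antibiotic entry in that record, and the protocol does not ask for course dates. The on-study instruction under Dietary Assessment covers diet and supplements only.

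**The concern.** The protocol treats a recent prebiotic or probiotic supplement as a reason to keep a woman out, but lets in a woman who has just finished an antibiotic course. Its own background cites a study, by title, of a probiotic countering bone loss after antibiotics through reduced intestinal dysbiosis. The link between antibiotics and the gut is therefore already within the trial's rationale.

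A woman who enters during recovery has a microbiota that moves for reasons unrelated to dried plum. If the movement continues through the roughly 14 weeks of the study, it differs between her two periods, and she is then not a clean control for herself. With about 27 completers, a few such women widen the confidence intervals for Objective 2 and could by chance fall mostly in one sequence. The exploratory regressions and mediation analysis use the same measurements and take on the same noise.

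**Working it through.** **1. The plan's own sample size, as background.** Section 11.0 gives n = 30, 10% attrition, 80% power, a standardised difference of 0.8 and alpha 0.05. Completers: 30 × 0.9 = 27. A paired t-test, taken as two-sided, with zero within-woman correlation (assumed, since none is stated) has effect 0.8/√2 = 0.566 on the SD of the difference. Power at n = 27 is 0.808, so the stated figure is reproduced. The point below does not depend on it.

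**2. What a course before entry does to the treatment contrast.** Write a woman's residual antibiotic offset at Visits 2, 3, 4 and 5 as a2, a3, a4 and a5, and the model's baseline slope as b. The offset left in her period 1 result is a3 − b·a2, and in her period 2 result a5 − b·a4. Her contribution to dried plum minus control is

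±[(a3 − b·a2) − (a5 − b·a4)],

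with a plus sign if plum comes first and a minus sign if it comes second.

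- If the offset is constant, the bracket is zero for any b.
- If it decays, the bracket is not zero. Under equal random allocation the sign is plus or minus with equal probability, so its expectation is zero and it adds variance.
- If one woman of 27 has a net drift of 2 SD (assumed), the mean difference moves by 2/27 = 0.07 SD. That is 0.07/0.8, about 9% of the effect the trial is sized for.

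The result is noise and possible chance imbalance, not bias.

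**3. How many women could be affected at entry.** The documents give no rate. For assumed shares of 5%, 10%, 20% and 30%, the expected number among 30 is 1.5, 3, 6 and 9. The chance of at least one is 1 − (1 − p)^30 = 0.79, 0.96, 0.999 and above 0.999.

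Suppose further that these women have k times the within-woman variance (assumed), and that a microbiota outcome has the same 0.8 effect with zero correlation. The variance is then multiplied by 1 − p + pk:

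| Share p | k | Variance factor | Power, 27 completers |
|---|---|---|---|
| 0 | – | 1.0 | 0.81 |
| 10% | 2 | 1.1 | 0.77 |
| 10% | 4 | 1.3 | 0.70 |
| 20% | 2 | 1.2 | 0.73 |
| 20% | 4 | 1.6 | 0.61 |

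**4. On-study exposure.** Let each end-of-period value be affected independently with probability p and shifted by s SD. Each value gains variance p(1 − p)s². At correlation 0.5 (assumed) the within-woman difference has variance 2(1 − 0.5) = 1.0 and gains 2p(1 − p)s². For p = 0.05 and s = 2: 2 × 0.05 × 0.95 × 4 = 0.38, and √1.38 = 1.17.

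| p | s = 2: variance | s = 2: standard error | s = 1: variance | s = 1: standard error |
|---|---|---|---|---|
| 3% | +23% | +11% | +6% | +3% |
| 5% | +38% | +17% | +10% | +5% |
| 10% | +72% | +31% | +18% | +9% |

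At zero correlation the base variance is 2, so 0.38 is a 19% rise, or about 9% in standard error (√1.19 = 1.09).

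This model assumes independent exposure in each period, which mostly means courses taken during the study. An entry exclusion cannot prevent those, so this table does not measure what the exclusion would gain.

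**The case against.** The strongest reply is that the design already deals with most of this. Stool and blood are taken at Visits 2, 3, 4 and 5, the models adjust for baseline and period, and sequence is randomised. An earlier course is thus partly absorbed by the Visit 2 and Visit 4 samples. Medication use is recorded and updated at every visit. The outcomes directly affected are secondary, and the mediation analysis is labelled exploratory. The supplement exclusion can also be read as keeping out exposures that duplicate the intervention, since the protocol describes dried plum as having prebiotic activity. On that reading, omitting antibiotics contradicts nothing the protocol states. Finally, the Phone Screening Questionnaire and the Medical History Form are not shown and may ask about antibiotics.

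Most of this stands and sets the size of the point. What it does not remove is recovery drift, which baseline adjustment cannot cancel when the offset changes between visits. An unseen form also cannot supply an exclusion that Section 4.0 lacks.

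A reader might infer more than the documents support:

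- **That antibiotic use biases the dried plum contrast.** Randomised sequence gives drift from a pre-entry course zero expectation, and nothing in the protocol suggests that dried plum changes antibiotic use.
- **That the variance rises show what the exclusion would save.** They rest on assumed rates and shifts and describe on-study exposure.
- **That the primary Th17 and cytokine results are compromised.** They are touched only through the proposed mechanism.
- **That the absence of an analysis rule for exposed periods is itself a defect.** Such a rule is commonly left to a statistical analysis plan, which is not at hand.

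**Conclusion.** The gap in Section 4.0 is real but modest. Recent systemic antibiotic use is not an exclusion in a trial whose second objective is microbiota and metabolite change and which already screens out prebiotic and probiotic supplements. The consequence is mainly lost precision in secondary and exploratory outcomes, with possible chance imbalance at about 27 completers.

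No size can be derived from the documents, because they give no antibiotic rate, shift, recovery time or within-woman correlation. Under the assumptions shown, the loss ranges from negligible (3% in standard error) to material (31%) for on-study exposure. For a 10% share of affected women at entry, power falls from 0.81 to between 0.77 and 0.70. The conclusion rests on the missing criterion, not on any one of these values. An eligibility criterion belongs in the protocol, so the absence of a statistical analysis plan does not excuse the gap.

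**What to change.** Two changes:

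1. In Section 4.0, add systemic antibiotic use to the existing 3-month bullet on prebiotic and probiotic supplements. The window is the protocol's own for that bullet. The documents give no separate basis for one specific to antibiotics, so the sponsor should confirm it.
2. In Section 8.0, under Health and Medical History, ask for start and stop dates of any antibiotic course at the updates already scheduled for Visits 2-5, so that exposed periods can be identified at analysis.

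The cost is one eligibility phrase, one dated field on an existing form and a slightly smaller screening pool. No visit, sample or procedure is added. The second change is recording only and places no restriction on treatment during the study.

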## 5.0 RECRUITMENT:

**Recruitment.** We will use several different strategies to recruit study participants. One source of participants that we will capitalize on are women who meet the age criteria who have previously undergone assessment in the Indiana Center for Musculoskeletal Health (ICMH), Musculoskeletal Function, Imaging and Tissue (FIT) Resource CORE and have indicated that they are interested in participating other research studies. We will also utilize the All IN for Health TrialX iConnect platform offered through the CTSI. Additionally, participants will be recruited through flyers and e-mail announcements to area community wellness programs, senior centers, churches and local clinics and doctors serving older adult populations. We will promote the study to different racial demographic groups so that the distribution of the study participants is reflective of the overall population of Indianapolis, IN. Women who are interested in volunteering for the study will be able to contact the Study Coordinator for the initial phone screening.

## 6.0 STUDY DESIGN:

We will conduct a randomized crossover control design trial with postmenopausal women with or without dried plum (*See Overview of Study Design Figure 1*). The study design will require participants to complete 5 visits to the IU Health University Hospital Clinical Research Center. Postmenopausal women, age 60-75 years, will be recruited to participate and undergo an initial phone screen to determine if they are potentially eligible to participate in the study (*See Phone Screening Questionnaire*). At Visit 1, a more extensive questionnaire involving relevant medical and health history will be completed focused on the inclusion/exclusion criteria, height and weight will be assessed. Volunteers who meet the inclusion/exclusion criteria and give informed consent to participate will be enrolled in the study. As a part of the consent process, volunteers will receive a separate informed consent that details the study tests and risk associated with participating in the Musculoskeletal FIT Core study (IRB study #1707550885). The FIT Core Study assessments will be completed at Visit 1 only. Importantly, this data will allow us to characterize the bone health and functional abilities of the study population. At the end of Visit 1, instructions will be provided for entering dietary data and stool sample collection, as well as a stool collection kit.

The primary study (Visits 2-5) is divided into three phases, with each lasting about 4 weeks (**Figure 1**). Prior to returning for Visit 2, participants will record their 24-hr dietary intake over three days using the Automated Self-administered 24-hour (ASA24) dietary assessment tool. At Visit 2, participants will return their stool sample, and baseline data collection will be performed that includes anthropometrics, questionnaires, any updates to the medical history questionnaire and a blood draw. Participants will then be randomly assigned to the AB or BA intervention sequence using a computer-generated list of random numbers. Instructions will be provided on the run-in protocol and incorporating dried plum into the diet (50 g/day or 5-6 dried plums per day) or not based on their sequence. Study personnel will provide the dried plums in snack packs at no cost. Note the snack packs will be provided by the California Prune Board. At Visit 3, participants will complete the data and sample collection as described for Visit 2 and then begin the washout period. Visit 4 will be scheduled following the washout period and the same procedures described in Visit 3 will be repeated with crossover to the second intervention. At Visit 5 (final visit), participants will complete the data and sample collection. At Visits 3 or 5, any remaining dried plums will be returned. All procedures will strictly adhere to the guidelines set forth by the Indiana University School of Medicine Institutional Review Board. The study will be registered with ClinicalTrials.gov.

**Figure 1. Overview of Experimental Design.** Postmenopausal women ( $n >= 30$ ) will be randomized to one of two treatment sequences (AB or BA) and complete 5 study visits (*details below*). Each treatment period (Phase 1 & 3) will consist of an approximately 1-wk run-in followed by 4 wks of treatment with a 3-4 wk washout in between.

